Our **Primary Specific Aim** is to examine cessation outcomes of a large-scale (N=1300; 20 participating clinics) randomized clinical trial of 1) Standard Care, based on established guidelines (Ask, Advise, Refer [quitline referral]) vs. 2) Standard Care + NRT Sampling. Participants will be drawn from a network of primary care settings that has established infrastructure in which to embed clinical research. Randomization will be at the clinic level, but individual participants represent the unit of analysis. Identified smokers who meet eligibility criteria will be consented into a trial. Interventions will be delivered within the primary clinic directly by providers who are trained and monitored on study procedures. All participants will receive advice to quit and referral to state quitlines. Half of the sample will receive a small token bag that includes samples (i.e., 1-2 week starter kit) of both nicotine patch and lozenge. Follow-up assessment (through 6 months) will track both primary (abstinence, quit attempts, use of additional treatment) and secondary (motivation, confidence) outcomes. Our team has strong experience in such trials, including methods to efficiently recruit and effectively retain large numbers of smokers in clinical research. Our principle hypotheses are as follows:

Hypothesis 1a: As compared to Standard Care model of physician-delivered brief advice (Ask, Advise, Refer), provision of brief advice + NRT samples within primary care setting will result in a higher abstinence rates (7-day, point prevalence at 6 month follow-up).

Hypothesis 1b: Brief advice + NRT sampling will result in longer period of abstinence (longest # days non-smoking) across the entire study duration.

Hypothesis 2: NRT sampling will result in higher rates of quit attempts (any self-defined and any 24hr quit attempt).

Hypothesis 3: Brief advice + NRT sampling will result in higher subsequent uptake of evidence-based treatment (behavioral, pharmacological assistance).

NRT sampling represents a brief, concrete, easy to explain strategy that both healthcare providers and smokers readily accept. Thus, it is uniquely suited to the primary care setting, and could be a novel, behaviorally based intervention to promote quitting. If so, NRT sampling holds great significance on both a clinical and policy level.

Human Subjects Research**1. Risks to Human Subjects****1.1 Human Subjects Involvement and Characteristics**

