4.1 Summary of the Protocol

The design calls for a 2-group, randomized clinical trial of 1) standard care (Ask, Advise, Refer) vs. 2) standard care + NRT sampling. Randomization will be at the clinic level, but the unit of analysis is the individual smoker. Following consent, baseline assessment, and provider intervention (all done within clinic), follow-up assessment (coordinated centrally through our study team) will continue at +1, +3, and +6 months. The primary outcome will be 7-day point prevalence abstinence at 6-month follow-up, though we track a number of other outcomes as well. A recent trial of comparative effectiveness for single/combined pharmacotherapy (79) provided strong framework for our decisions. As a comparative effectiveness study, our guiding philosophy is to optimize ecological (i.e., external) validity, while at the same time maintaining basic standards of scientific rigor.

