as the covariate, estimated using generalized estimating equations (GEE) to account for clustering within clinic. Rates for each outcome will be estimated along with its 95% confidence interval. The coefficient on group will be evaluated using a Wald test to determine if the abstinence rates in the two arms are statistically significantly different at the one-sided 0.025 level. Additional regression modeling will be performed where covariates such as age, gender, and race are accounted for. We will also consider interactions between NRT and categorical covariates to determine if there are certain subgroups in which NRT sampling is more or less effective. Though we expect few individuals to make more than one quit attempt over the span of 6 months, and thus examine incidence of quit attempts (Hypothesis 2), we will examine the distribution of quit attempts, and if appropriate, examine number of quit attempts via Poisson regression modeling. In addition to binary outcomes of treatment uptake (Hyp. 3), we will test for continuous outcomes (e.g., treatment intensity, duration) via GEE regressions.

Hypotheses 1b Hypothesis 1b predicts that provision of NRT samples will result in longer period of abstinence (longest # days non-smoking) across the entire study duration, and will be evaluated using regression modeling via GEE accounting for clustering by clinic.

Secondary Analyses

Provider Acceptability We will provide separate, descriptive data on provider acceptance and satisfaction with treatment delivery. We do not plan any formal between group comparisons because of very limited sample size (14 clinics in each site). This study is not powered on provider-level outcomes of our intervention, but such data will be useful as we consider expanding our intervention into different venues.

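### Section 4.9 tests a clinic-randomised effect with a GEE Wald test but names no standard error, reference distribution or degrees of freedom; run in the usual way with 20 clinics, the one-sided level is about 0.040, not 0.025

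*Combined protocol and SAP*

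**What the plan says.** Specific Aims and section 4.1 both make the clinic the unit of randomisation and the smoker the unit of analysis; 4.1 reads "Randomization will be at the clinic level, but the unit of analysis is the individual smoker". Specific Aims and section 2.1 give 20 clinics. The clinic-selection text ahead of section 4.6 makes 20 the minimum.

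For Hypotheses 1a, 2 and 3, section 4.9 specifies logistic regressions with treatment group as the covariate, "estimated using generalized estimating equations (GEE) to account for clustering within clinic". It continues: "The coefficient on group will be evaluated using a Wald test", to decide whether the arms are "statistically significantly different at the one-sided 0.025 level". It also promises intervals: "Rates for each outcome will be estimated along with its 95% confidence interval". Hypothesis 1b "will be evaluated using regression modeling via GEE accounting for clustering by clinic", with no test or level named.

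The visible text of 4.9 does not say whether the standard error is robust or model-based, whether a small-sample correction is applied, which working correlation is used, or whether the Wald statistic is referred to a normal or a t distribution.

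**The concern.** A GEE sandwich variance is justified when the number of clusters is large. Here the effect of interest varies only between clinics, so its precision is estimated from about 20 independent units, not 1300. Two things then go wrong with an uncorrected sandwich and a normal reference. The variance estimate is too small on average, and its own sampling error is ignored. Both push the false-positive rate above the stated level.

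Hypothesis 1a, 7-day point prevalence abstinence at 6 months, is the outcome on which the study is powered (4.2), so the error rate of the main claim is at stake. Hypotheses 2 and 3 use the same test.

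**Working it through.** **Inputs from the documents.** One-sided level 0.025 (4.9); 20 clinics and N = 1300, so 65 per clinic on average (Specific Aims); base abstinence 15% (4.13); power 0.80 (4.17).

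**Assumptions.** Ten clinics per arm, inferred from 20 clinics and the statement in Specific Aims that half the sample gets the samples. The intraclass correlation (ICC) is not given, so 0.001 to 0.05 is used. The Provider Acceptability paragraph of 4.9 still speaks of 14 clinics, so 28 clinics is also computed.

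**The stated level.** 1 − Φ(1.960) = 0.025. The figure is right as a limit for many clinics.

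**Closed form.** With m equal clinics per arm and only a clinic-level covariate, the uncorrected sandwich variance averages (m − 1)/m of the true variance and carries about 2m − 2 degrees of freedom. The actual one-sided level is therefore

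P( t(2m−2) > 1.960 × √((m − 1)/m) ).

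- m = 10: 1.960 × √0.9 = 1.859, and P(t18 > 1.859) = 0.0397, so 0.0397/0.025 ≈ 1.6.
- m = 14: 1.960 × √(13/14) = 1.889, and P(t26 > 1.889) = 0.0351.

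For 20 clinics the two defects separate as follows:

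| Standard error | Reference | Level |
|---|---|---|
| Uncorrected | normal | 0.0397 |
| Bias-corrected | normal | 0.0328 |
| Uncorrected | t18 | 0.0308 |
| Bias-corrected | t18 (critical value 2.101) | 0.0250 |

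**Simulation.** Beta-binomial data under the null, 15% abstinence, 100,000 runs per setting:

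- 20 clinics of 65: 0.038 to 0.042 over the ICC range.
- 28 clinics: 0.034 to 0.035.
- Exchangeable GEE with robust standard error, fitted in standard software (1,200 runs each, Monte Carlo error about 0.004): 0.041 at ICC 0.01 and 0.039 at ICC 0.02.
- Exchangeable model-based standard error with normal reference: 0.038 to 0.044. If the estimated correlation is floored at 0, the level runs from 0.025 (ICC 0.001) to 0.041 (ICC 0.05).
- Hypotheses 2 and 3, at assumed rates of 25% and 50%: 0.039 to 0.044.

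**Unequal clinics.** The timetable in 4.6 gives cumulative totals of 116, 406, 754, 986 and 1300 for 2, 7, 13, 17 and 20 clinics. If patients are counted in the year their clinic starts, that is 116/2 = 290/5 = 348/6 = 232/4 = 58 per clinic for the first 17, then 314/3 ≈ 105 for the last three. Those sizes (coefficient of variation 0.26) give 0.040 to 0.045. With hypothetical coefficients of variation of 0.5 and 0.8, an independence working correlation and ICC from 0 to 0.05, the level is 0.042 to 0.048 and 0.046 to 0.059.

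**Intervals.** For one arm's rate with 10 clinics, coverage is 1 − 2 × P(t9 > 1.859) = 0.904. Simulation gives 0.902 to 0.907 with equal clinics and 0.893 to 0.904 with the timetable sizes.

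**Power.** If 0.80 came from a normal reference, the noncentrality is 1.960 + 0.842 = 2.802. With an unbiased variance and t18, P(T > 2.101) = 0.755; with 28 clinics (t26) it is 0.769.

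**The case against.** The strongest reply is that 4.9 contains an unstated option and no error. Clustering is addressed, nothing written there is false, and a corrected standard error with a t reference is still a Wald test. That is true: 0.040 follows from one reading and is not a figure the plan adopts. But with nothing more said, a GEE Wald test is normally run as a z-test on the robust standard error. A plan that allows either 0.025 or 0.040 on its primary hypothesis has not fixed its error rate.

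Section C.10 of the grant text is not available. Section 4.4 cites it for the sample-size rationale, and it may say more. The point is therefore limited to 4.9.

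A model-based exchangeable standard error with the correlation floored at 0 stays near 0.025 when the ICC is close to 0.001. This stands, so the insensitivity to ICC belongs to the sandwich and unfloored readings. Even floored, the level reaches 0.041 at ICC 0.05.

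The timetable sizes are doubtful. Its footnote assumes an average of 58 per clinic, and 20 × 58 = 1160, not 1300. The 105 may be an unreconciled total. The 0.0397 does not depend on it.

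Section 4.9 also lets baseline imbalances into the regressions, whereas the main figures are for the unadjusted model. A linear check on clinic means with one to three clinic-level covariates gave 0.045 to 0.060 uncorrected, and 0.026 to 0.031 with the Kauermann-Carroll correction and t18. Adjustment makes the uncorrected test worse and leaves the corrected one slightly liberal.

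**Conclusion.** The concern holds. As written, 4.9 does not secure its one-sided 0.025 level. Under the usual reading with 10 equal clinics per arm, the level is about 0.040 (0.035 with 28 clinics), and it rises as clinic sizes become more unequal. Nominal 95% intervals for the rates would cover about 90%. The result rests on the inferred 10/10 split and on an uncorrected sandwich or unfloored model-based standard error with a normal reference. For equal clinics with the sandwich, it hardly depends on the ICC. Because this is the primary test, the choice must be written down before the data are analysed.

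**What to change.** In 4.9, name the working correlation, a bias-corrected sandwich standard error, and a t reference on the number of clinics analysed minus 2 (18 with 20 clinics). Choose one correction now, before enrolled sizes are known:

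- **Kauermann-Carroll** holds 0.024 to 0.026 with equal clinics and 0.025 to 0.028 with the timetable sizes. In a hypothetical scenario with sizes from 30 to 143 it drifts to 0.026 to 0.034.
- **Mancl-DeRouen** is safer if sizes may vary that much (0.020 to 0.023 in the same scenario), but it is conservative otherwise (0.019 to 0.022).
- **A clinic-level permutation test** that follows the actual randomisation scheme is an alternative (0.021 to 0.024).

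Apply the same method to Hypotheses 1b, 2 and 3, and state the test and level for 1b. Say how clinic-level covariates, if any enter the model, change the degrees of freedom. For an arm's rate, base the interval on that arm's clinics (9 degrees of freedom with 10 clinics). Kauermann-Carroll with t9 then covers 0.949 to 0.952 with equal clinics and 0.942 to 0.951 with the timetable sizes.

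Sections 4.13 and 4.17 name no test for the efficacy look. If it uses this Wald test, the same correction is needed there, since fewer clinics will contribute. As an illustration only, with 12 clinics (6 per arm) and 0.005 taken as two-sided, P(t10 > 2.807 × √(5/6)) = 0.014 against 0.0025.

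The cost is some wording, one software option and a restated power. Against 0.80 with a normal reference, simulated power is 0.75 to 0.76 with Kauermann-Carroll, 0.71 to 0.73 with Mancl-DeRouen and 0.74 to 0.77 with the permutation test.

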1.3 Potential Risks

The research protocol calls for non-treatment seeking smokers, who will vary across the motivational spectrum from wanting to quit vs. not wanting to quit, to receive standard care (Ask, Advise, Refer) or NRT sampling. The sampling intervention consists of a two-week supply of both nicotine patch and lozenge, both over-the-counter products that have received extensive support for their efficacy and safety (19, 97-102). Nonetheless, there are potential for risks for each product alone, as well as when used concurrently. We believe these risks, described below, will be minimal and mild.

1.3.1 Nicotine lozenge In a prior trial of the particular lozenge we will be using, 68% and 71% of 2 and 4 mg users of nicotine lozenge reported an adverse event (AE) vs. 54% of placebo users (103, 104). With both active doses of the lozenge, 7% dropped out due to AEs and 7% dropped out due to AEs on placebo. With both active doses, 1.6% reported a serious AE which was not different than that for placebo. There were no deaths or irreversible injuries deemed possibly due to lozenge. The most common AEs were nausea, flatulence and upper respiratory tract infection (103). The current labeling on OTC lozenge states pregnant and breast feeding women, those less than 18 years of age, those using a prescription medication for depression or asthma or a smoking cessation medication and those with heart disease, recent heart attack, irregular heartbeat, high blood pressure not controlled by medication, stomach ulcers or diabetes should consult a provider before using the lozenge.

In a recent trial of placebo vs. single vs. multiple medications for smoking cessation (85), the three most common adverse events within the lozenge group were 1) nausea: 7.8%, compared to 4.4% within placebo group, 2) mouth/throat irritation: 6.7%, compared to 3.3% within placebo group, and 3) hiccups: 6.2%, compared to 0.3% within placebo group. All other adverse events occurred <5%. In our recent trial of sampling nicotine lozenge, which was not placebo-controlled but was based on a similar sampling strategy as proposed here, the most common adverse events were nausea (23% of all adverse events), throat irritation (17%), and hiccups (13%).

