4.9 Data Analysis Plan

All analyses are based on an intent-to-treat approach, and are nearly identical to analyses from our current and prior studies. Exploratory analysis will be performed on all variables to determine if transformations are needed. Any significant baseline differences between groups will be included in regression analyses described below. All analyses below will be run separately for full intent-to-treat sample (immediately below), per protocol, and, within the NRT group, using those participants who used single vs. combined NRT products.

Examination of Potential Site Differences Outcomes and patient characteristics will be estimated across clinics using summary statistics and confidence intervals. This will be considered an exploratory analysis due to the relatively large number of clinics and, hence, the large number of multiple comparisons that could arise. Grouped logistic regression modeling may be used to describe associations between clinic characteristics and binary clinical outcomes (e.g., quit rate).

Missing Data & Dropout The most conservative approach for handling missing data is to substitute them with baseline values, assuming outcomes have all returned to baseline, with no quit attempts made or abstinence achieved. If this assumption is incorrect, it biases the results towards the null by reducing between group differences. Since we expect few missing data, we will use this approach. If missing data >10%, we will calculate results using this conservative method but also using methods in which missing data are imputed as described in the SRNT guidelines. We will also assess whether dropout is differential by study group. In our current and recent studies of cessation induction, this has not been the case. Abstinence will be reported both with and without (missing samples) cotinine verification.

Hypotheses 1a, 2, & 3 These hypotheses predict that provision of NRT samples will lead to higher abstinence rates (Hyp. 1a), incidence of quit attempts (Hyp. 2), and uptake of additional treatment (Hyp. 3). Logistic regressions will be performed for each outcome with treatment group (standard care vs. NRT sampling)

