Cost Effectiveness We will track intervention delivery costs (i.e., personnel, materials, NRT itself) per treatment group, though anticipate the only difference to be the cost of NRT. We will analyze and compare costs for intervention and control patients, for quit attempters vs. non-quit attempters, and for quitters vs. non-quitters. We will do this both across and within groups, and our model will adjust for patient characteristics, including demographics and smoking history. Led by our dissemination expert ([name]), we will examine differences in direct medical costs (from the EMR) of all medical care post study enrollment for a sample of all study participants, of all participants who quit smoking during the trial, and for all intervention participants. We expect to show that NRT sampling as a strategy is, at least in the short term cost neutral, if not cost saving.

Other We will also examine changes in cigarette smoking, motivation, confidence, attitudes/knowledge of NRT over time, as a function of treatment group. These continuous variables (absolute, and change since baseline) will be examined as per Hypothesis 1b above.

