4.10 Quality Assurance Plan

Data will be collected centrally by our research staff rather than locally at each clinic. Computerized data collection methods (Redcap) optimize quality assurance. Redcap system does not accept outliers, illogical response patterns, etc. The PI will have weekly meetings with the research assistants to discuss qualitative comments received during data collection and any problems in data collection. The statistician will periodically examine the database to look for irregularities. Initial data analyses will examine distributions of variable scores, comparability of baseline characteristics, follow-up rates and use of extra-study cessation treatment across conditions in case analyses need to be adjusted for these.

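### No efficacy model prespecifies a prognostic baseline covariate, and the continuous outcomes are planned as absolute and change scores, so some precision is given up

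*Combined protocol and SAP*

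**What the plan says.** All of this is in the combined protocol and SAP.

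- **Main models, Hypotheses 1a, 2 and 3 (section 4.9).** "Logistic regressions will be performed for each outcome with treatment group (standard care vs. NRT sampling", with the group term entered "as the covariate, estimated using generalized estimating equations (GEE) to account for clustering within clinic". The Wald test on that coefficient, one-sided 0.025, is the efficacy test.
- **Supporting models (4.9).** "Additional regression modeling will be performed where covariates such as age, gender, and race are accounted for".
- **Hypothesis 1b (4.9).** A GEE regression clustered by clinic. No covariate is named.
- **Conditional adjustment.** 4.9 states "Any significant baseline differences between groups will be included in regression analyses described below". Section 4.10 says initial analyses will look at "comparability of baseline characteristics, follow-up rates and use of extra-study cessation treatment across conditions in case analyses need to be adjusted for these".
- **Continuous secondary outcomes (4.9, Other).** For cigarettes smoked, motivation, confidence and attitudes to NRT: "These continuous variables (absolute, and change since baseline) will be examined as per Hypothesis 1b above".
- **Cost model (4.9, Cost Effectiveness).** Here "our model will adjust for patient characteristics, including demographics and smoking history". This is the only model that names smoking history.
- **Population (1.3).** Participants are smokers "who will vary across the motivational spectrum from wanting to quit vs. not wanting to quit".

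**The concern.** A baseline variable that predicts quitting can sharpen the arm comparison, and the plan appears to hold three candidates. Change since baseline cannot be computed for cigarettes, motivation and confidence unless all three are recorded at baseline. The 50% reduction outcome in section 4.2 also needs baseline consumption. The plan expects wide variation in motivation, yet the only covariates it names for efficacy are age, gender and race.

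Clinics are the randomised unit and there are only 20 of them. Chance differences between clinics in motivation or smoking therefore feed into the error of the arm contrast. Prespecified adjustment removes that noise to the extent that the covariates predict the outcome. For the continuous outcomes the baseline value is usually the strongest predictor available, and neither an absolute nor a change score makes the best use of it.

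What is at stake is precision and a model fixed in advance. Bias and type I error are not in question.

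**Working it through.** **Inputs from the documents.** N = 1300 (4.4); 20 clinics, randomised by clinic (Specific Aims); control abstinence 15%, power 0.80 falling to 0.79 with the interim look (4.13); one-sided 0.025 (4.9). I use 1300/20 = 65 per clinic.

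**Assumed, because the documents do not give them.** Treated rate 22%, clinic variation, covariate strength, and baseline/follow-up correlation r.

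**1. The plan's own figures.** N = 1300 cannot be rebuilt, because the projected effect and ICC are in a grant section that is not supplied. From 15%, 650 per arm at 80% power detects 21.0% with no clustering, 22.8% at ICC 0.01 (design effect 1 + 64 × 0.01 = 1.64) and 25.7% at ICC 0.03 (design effect 2.92). The size is neither confirmed nor refuted. The interim figures agree with the plan: a two-look O'Brien-Fleming design gives an interim level of 0.0052 (stated 0.005) and power 0.797 (stated 0.79).

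**2. Abstinence, simple approximation.** If covariates explain a share R² of the variance, power moves from 0.80 to Φ(2.80/√(1 − R²) − 1.96). The equivalent number of extra patients is 1300/(1 − R²) − 1300.

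| R² | Power | Equivalent extra patients |
|---|---|---|
| 0.01 | 0.804 | 13 |
| 0.02 | 0.808 | 27 |
| 0.05 | 0.820 | 68 |
| 0.10 | 0.840 | 144 |

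**3. Abstinence, simulation.** Settings: 20 clinics × 65, 15% against 22%, clinic SD 0.18 on the logit scale, cluster-robust logistic models with t on 18 df, one baseline covariate with no clinic-level variation, 2,000 runs per setting. Compare within rows.

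| Covariate OR per SD | Power without → with covariate | SD of log OR | Variance of risk difference, adjusted/unadjusted |
|---|---|---|---|
| 1.5 | 0.786 → 0.790 | 0.168 → 0.170 | 0.976 |
| 2.0 | 0.816 → 0.824 | 0.161 → 0.167 | 0.943 |
| 2.5 | 0.812 → 0.842 | 0.161 → 0.175 | 0.927 |

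The spread of the log odds ratio does not fall. Power rises because the conditional estimate is larger. At OR 2.0 its mean goes from 0.472 to 0.505, so estimate/SD goes from 0.472/0.161 = 2.93 to 0.505/0.167 = 3.02. On the risk-difference scale the gain is a smaller variance.

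**4. Abstinence, covariate that also varies between clinics.** With a clinic ICC of 0.01-0.10 for the covariate itself and clinic SD 0.2 or 0.3, the ratio of unadjusted to adjusted risk-difference variance was 1.02-1.13 at OR 1.5 and 1.05-1.31 at OR 2.0. By Φ(2.80√ratio − 1.96), a power of 0.80 becomes:

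- ratio 1.03: 0.81
- ratio 1.15: 0.85
- ratio 1.31: 0.89

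Ratios near 1.3 appear only when OR 2.0 and ICC 0.10 are combined.

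**5. Continuous outcomes.** With equal variances at baseline and follow-up, the variances relative to the absolute score are 1 (absolute), 2(1 − r) (change) and 1 − r² (follow-up adjusted for baseline). The ratio of adjusted to change is (1 + r)/2.

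| r | Adjusted/absolute | Adjusted/change |
|---|---|---|
| 0.3 | 0.91 | 0.65 |
| 0.5 | 0.75 | 0.75 |
| 0.7 | 0.51 | 0.85 |

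The saving is 9-49% against absolute scores and 15-35% against change scores. It applies to the individual-level component at a single follow-up time.

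**The case against.** The strongest reply is that the plan is sound and more flexible than a quick reading suggests. Much of that stands.

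- **Open list.** A reader might infer that the plan adjusts for nothing, or for age, gender and race alone. The documents do not support that. Those three are introduced as examples, and 4.9 and 4.10 would bring in baseline smoking, motivation or confidence if they were significantly unbalanced or a comparability check called for it. But this is selection by imbalance, not by prognostic value. A strong predictor with a non-significant imbalance stays out, and the model is not fixed beforehand.
- **Validity.** A treatment-only GEE is an acceptable primary analysis, and nothing here shows bias. This stands in full.
- **Mediators are not baseline predictors.** The abstract and aims present motivation and confidence as things that sampling changes. That does not establish that their baseline values predict six-month abstinence. This also stands: prognostic strength is plausible but is not given in the documents.
- **Scale.** The plan tests a log odds ratio, whose spread does not fall on adjustment. This is correct, and it is why a standardised risk difference belongs in the fix.
- **Silence on continuous outcomes.** The plan does not say whether baseline could be a covariate or a repeated measure in the GEE. It is fair to say only that baseline is not named as a covariate, not that it was deliberately excluded.
- **Baseline measurement.** The questionnaire's content is not shown. That it covers motivation and confidence is inferred from the planned change scores, which is a fair inference.

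**Conclusion.** The point holds as a matter of efficiency and prespecification. No efficacy model for Hypotheses 1a, 1b, 2 or 3 commits in advance to a prognostic baseline covariate, and the continuous outcomes are planned without naming baseline as one.

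For abstinence the likely cost is about 0 to 4 power points, for assumed R² of 0.01 to 0.10. A reader might infer from the largest simulated figure that adjustment would lift power from 0.80 to 0.89. That needs a strong covariate and high clinic-level variation together, and the documents supply neither value. For continuous outcomes the loss is clearer, 9-49% or 15-35% of variance depending on the comparator, but it rests on assumed correlations of 0.3 to 0.7 and concerns secondary outcomes. The change is worth making because it is nearly free, not because the planned analysis is wrong.

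**What to change.** In section 4.9:

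1. Prespecify baseline cigarettes per day, motivation and confidence as covariates in the Hypothesis 1a, 1b, 2 and 3 models, entered whether or not the arms differ on them.
2. For the binary outcomes, report the standardised risk difference beside the odds ratio, with clinic-level clustering respected in both.
3. Keep the treatment-only model as a sensitivity analysis.
4. For cigarettes per day, motivation, confidence and attitudes, replace the separate absolute and change analyses with one analysis of the follow-up value adjusted for its baseline.

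The cost is SAP wording and a line of model code, with no new data if the three variables are on the baseline questionnaire as inferred. There are two small downsides. A few degrees of freedom are spent with about 20 clinics, which is why the list stops at three terms. The adjusted odds ratio is conditional rather than crude, which the standardised risk difference addresses.
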